In work stream 1 we conducted detailed research to define the symptom burden and needs of people with severe memory problems at the end of life, and their family carers. We have undertaken a longitudinal cohort study and have recruited 61 people with severe memory problems (FAST stage 7a and above, doubly incontinent and speaks only 5-6 words per day), 57 residing in care homes and four in their own homes. We have also recruited 26 of their family carers. Results from these studies showed how people with severe memory problems have multiple unmet needs, particularly with regards to management of pain and agitation. They are at high risk of pressure sores and have problems with eating and swallowing. There is lack of individual care planning and consideration of end of life care needs.

Work stream 2

Workshops with health and social care professionals

In work stream 2 in a first cycle of workshops we included a wide range of stakeholders and participants at all levels of responsibility. We conducted two workshops in London and one in each of Edinburgh, Solihull and Belfast. We used clinical vignettes describing people with severe memory problems and asked participants to consider how their care could be enhanced to provide solutions to the issues described.

In a second round of workshops we enhanced the content and face validity of our intervention, by using the RAND/UCLA approach (18). A key aspect of this approach is the Rand Appropriateness Method (RAM) which was used as a way to agree the key components of the intervention. To ensure that we took proper account of context further workshops were held across the four countries of the UK (sites in London, Edinburgh, Solihull, Belfast and Penarth). Before each workshop an online process managed by Survey Monkey, asked stakeholders to rank, for appropriateness, statements describing possible intervention components that were derived from the first round of workshops. Results were then analysed before each workshop and any points of disagreement were discussed further in the

workshop. Following this, participants were asked to rank statements describing components for necessity but independent of economic considerations. Data from all the workshops were pooled and a final bank of statements describing potential components of the enhanced model of care derived.

Interactive qualitative interviews with family carers and healthcare professionals

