8. Referrals and multi-disciplinary team working/ single point of contact, continuity of general practitioner (GP) care, rotating staff across environments to bring new learning, out of hours care from GP's who know patients.

The likelihood of successful implementation of our new enhanced care model requires that we understand the sociological theory underlying how our intervention would operate in practice (19). Following the RAM process, we scrutinised retained intervention components and mapped them to the theories described by Grol (19), categorising them according to which of the four operational levels identified by Ferlie and Shortell (20) and others such as Greenhalgh (21). We thought the components might operate on; 1) individual, 2) team, 3) group and 4) system levels. We explored both impact and process theories, operational and utilisation plans at the levels of the individual, social interaction, organisational context and economic/political context.

Details of the enhanced model of care for piloting are presented below (page 16 and Appendix 1).

AIMS AND OBJECTIVES OF PILOT STUDY

Our aim is to conduct a naturalistic pilot study to understand how the Compassion enhanced model of care operates in practice in two care homes in two different health and social care economies; one in the Camden Commissioning Group and one in the Barnet Commissioning Group.

Objectives

In the pilot study we will provide a coordinator with clinical skills- an “Interdisciplinary Care Leader (ICL)” who will coordinate and support the existing team of health and social care professionals working with participating care homes to enhance the management of people with severe memory problems. Our objectives will be met by collecting both quantitative data and qualitative data from the enhanced care team, care home staff and family caregivers

Specific objectives of the pilot study will be to:

1. Understand whether the enhanced model of care is feasible in the setting
2. Determine whether the enhanced model of care is acceptable to staff and family carers of people with severe memory problems in the care home
3. Understand facilitators and barriers to the implementation of the enhanced model of care by collecting qualitative data from paid and family carers on the experience of the intervention

4. Evaluate whether the enhanced model of care has an impact on a range of national key performance indicators and outcomes including those operating at a number of levels:

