team their contact details so the research team can contact them regarding the study. If the family carer does not give permission for the care home to give their details to the research team, no further contact will be made. If permission is granted a member of the research team will telephone the family carer. If the consultee agrees to the person taking part they will be sent a family carer assent form to sign or invited to visit the care home to meet with the research team to do this in person. If no assent form is returned within 14 days then the research team will telephone the personal consultee to see whether they are still interested in participating.

5. If a) no friend or next of kin that can act as a personal consultee is documented in the clinical notes, or, b) after three attempts at telephone contact over one week by the care home manager, they are unable to contact a personal consultee, then the research team will use a professional consultee. This will be defined as a senior experienced health or social care worker who is not directly involved in the research or care of the patient. Through the cohort study we have identified skilled professionals within each CCG who are not involved in the research project or in the patient's direct clinical care and are happy to act in this role. These "consultees" will be given information about the study and training on their responsibilities by the research team. They will follow a structured procedure to give assent for the person's participation in the study and sign their assent for this.

Figure 1. Summary of consent procedures for the collection of individual level outcome data

Recruitment of family carers to give information for the evaluation

We wish to evaluate the opinions of family carers of residents with severe memory problems who have received the enhanced care service. We will only recruit carers of people with severe memory problems who have already entered the study as the recruitment of dyads will enable us to link the experiences of people with severe memory problems and their family carers.

Family carer inclusion criteria

- If the resident with severe memory problems does not have capacity this will be the main family carer (e.g. family member or friend in regular contact and who is the next of kin or a 'key decision maker', identified by the care home manager). If the resident does have capacity we will ask them to nominate who they think is their family carer.

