After full data collection ends, we will undertake definitive analyses to detail the demographic features of the cohort and assess the symptom management and their health care needs (using Stirling, Waterlow, NPI and sentinel events), taking into account repeated measures on individual subjects. We shall describe the level and nature of unmet needs and examine descriptively (using mean and standard deviations or suitable alternatives in case of non-normally distributed data and graphs) how comfort and quality of life change over time (using PAINAD, SM-EOLD, SW-EOLD and QUALID). We will describe the trajectory of carer wellbeing (HADS and Zarit Buden Interview) during their friend/relative's final stages of life with severe memory problems and how this may change if the resident dies, using plots of the of wellbeing over time.

Sample size

This is a pilot study and as such a formal power calculation is not appropriate. Numbers are chosen on pragmatic grounds as sufficient to demonstrate feasibility in terms of recruitment and acceptance of the intervention. We will aim to recruit 30 residents with severe memory problems from two care homes from which to collect individual outcome data.

Health economics

Health economic evaluation will consider resource allocation in caring for patients with severe problems and, where relevant, in their last 6 months of life, as well as the quality of life of their family carers and associated economic impact on these family carers in this period.

Data on resource and service use for people with severe memory problems (RUD-Lite) and economic burden on family carers (Zarit Burden Interview) will be collected both at baseline and monthly after the enhanced care project has been implemented. These data will be collated with unit costs data from *Unit Costs of Health and Social Care (2012)* (47;48) to obtain costs per patient from NHS (such as averted hospital admission, costs for a typical episode), costs from personal social services (such as training and education for care home staff) and costs from societal perspectives (such as local commissioners' decisions on scarce resource allocation, additional costs to public purse where caring responsibilities had been met by the state instead of family carers).

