Economic evaluation of the quality-adjusted life years (QALYs) for family carers will utilize EQ-5D-5L instrument to assess if enhanced care project has resulted in greater utility attained for this group and associated cost-effectiveness.

PROJECT MANAGEMENT

Registration, sponsorship and indemnity

The project will be registered with the research departments at the participating CCG. University College London will be the project sponsor and provide insurance. The research team will obtain honorary clinical contracts for each participating CCG, adhering to the Marie Curie Palliative Care Research Unit's Lone Worker Policy (2012).

Data protection

Case Report Forms (CRF) for the study will be stored in accordance with the Declaration of Helsinki. Electronic data will be anonymised and stored on a password protected database. At the end of the study anonymised files will be stored securely in a secure UCL archiving facility.

Research network support

The programme has been adopted by the DeNDRoN (Dementias and Neurodegenerative Diseases Network)

Project Staffing

The person appointed to the ICL post will have extensive experience in the care of older people and their family carers in care home settings and with expertise in severe memory problems and social care. They will deliver the intervention with the core team. They will be supervised by the PI ([name]) and, given the nature of the work, offered supportive clinical supervision by [name]. The ICL will receive training to acclimatise them to the care homes in which they will be working and familiarise them with the intervention manual. They will have a monthly meeting with the project team to check adherence to the principles of the manual and to make any necessary adaptations to this. Two clinical researchers, from the Marie Curie Palliative Care Research Unit, who have extensive clinical and research experience with both palliative care and people with severe memory problems and family carers will collect the individual data for the evaluation of the enhanced care intervention. The researchers have particular skills in interviewing bereaved family carers and relatives.

Core study team

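### The economic analysis is set to judge whether the project raised carer utility and is cost-effective, but the design has no concurrent control and names no comparator for carer utility or costs

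*Protocol*

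**What the plan says.** The Health economics section states the purpose of the carer QALY analysis: "to assess if enhanced care project has resulted in greater utility attained for this group and associated cost-effectiveness". The same section gives "averted hospital admission" as an example when it describes NHS costs per patient.

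The aim of the study is to "conduct a naturalistic pilot study to understand how the Compassion enhanced model of care operates in practice in two care homes". The section on consent for implementing the model says that the intervention is applied to the whole home. No usual-care home, arm or period is described.

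On numbers, the Sample size section says "This is a pilot study and as such a formal power calculation is not appropriate" and "We will aim to recruit 30 residents with severe memory problems from two care homes". No carer target is given. Carers enter only as part of a dyad: "We will only recruit carers of people with severe memory problems who have already entered the study".

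Table 4 schedules the carer EQ-5D-5L at project start, monthly, and after death or in bereavement. It lists no EQ-5D-5L for residents. The Quantitative analysis section plans a comparison with the programme's previous study, directly after naming SWEOLCD and QUALID. Objective 5 is to describe delivery costs, which may then be set against potential benefits.

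**The concern.** A cost-effectiveness statement is incremental: it needs costs and effects under the intervention and under an alternative. A statement that a project produced a utility gain needs the same contrast on the effect side. The protocol commits to both conclusions, but for carer utility and for costs it describes only repeated measurement of people who are all exposed to the intervention.

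If the analysis is run as worded, any rise or fall in carer utility over six months would be read as the project's effect. Residents in this population are expected to decline and some to die, and the protocol itself expects carer wellbeing may change after a death. A true benefit could be hidden by bereavement, or natural recovery and adjustment could be credited to the project. Because Objective 5 envisages costs being set against benefits and recommendations made, an unsupported cost-effectiveness figure could carry more weight than a pilot result should.

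**Working it through.** **Step 1. Is there a comparator for the quantities in the claim?**

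| Quantity | Measured in | When | Comparison named |
|---|---|---|---|
| Carer utility (EQ-5D-5L) | Carers of enrolled residents | Start, monthly, after death | None |
| Resource use (RUD-Lite) | Enrolled residents, including informal care | Start, monthly | None |
| Carer burden (Zarit) | Same carers | Start, monthly | None |
| Symptom burden and quality of care (SWEOLCD, QUALID) | Enrolled residents and their carers | Start, monthly | Previous study |

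Only the last row has an outside reference. The protocol does not say that the previous study collected EQ-5D-5L or that its costs will be used. For carer utility and costs, the only available contrast is each person's later values against their own start value.

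**Step 2. What does that contrast estimate?** It is the sum of any project effect, the effect of the resident's decline, the effect of bereavement where a death occurs, and any time trend. With both homes exposed from the start, nothing in the design separates the first term from the others.

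**Step 3. Do costs and effects cover the same people?** EQ-5D-5L is listed for carers only. QUALID is used for residents, but it is described as a quality-of-life scale and no utility weights are mentioned. Costs cover residents' service use and also carers, through informal care and economic burden. A ratio of these costs to carer QALYs would leave any resident benefit or harm out of the denominator.

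**Step 4. Precision.** The 30 residents were chosen on pragmatic grounds, so there is no stated calculation to reproduce. The number of carers has to be assumed.

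- Earlier cohort (Work stream 1): the programme reports that it "have recruited 61 people with severe memory problems", and "We have also recruited 26 of their family carers". Rate = 26/61 = 0.426.
- Expected carers = 30 × 0.426 = 12.8, about 13.
- Exact 95% CI for 26/61 is 0.300 to 0.559. Times 30, this gives 9.0 to 16.8, so about 9 to 17. The ceiling is about 30, one main carer per resident.
- 95% CI half-width for a mean within-carer change, in SD units = t(n−1, 0.975)/√n.

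| Carers | Half-width (SD) | If SD of change is 0.10 | If SD of change is 0.25 |
|---|---|---|---|
| 9 | 0.77 | 0.08 | 0.19 |
| 13 | 2.179/3.606 = 0.60 | 0.06 | 0.15 |
| 17 | 0.51 | 0.05 | 0.13 |
| 30 | 0.37 | 0.04 | 0.09 |

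The SD range of 0.10 to 0.25 is an assumption; the protocol gives none. The figures ignore attrition and clustering within two homes.

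**Step 5. Would the earlier cohort rescue the analysis?** Suppose its 26 carers had EQ-5D-5L and served as controls, which is not planned. The change detectable with 80% power at two-sided 5% would be (1.960 + 0.842) × √(1/13 + 1/26) = 2.802 × 0.340 = 0.95 SD. The two groups would also differ in entry stage (FAST 7a and above, against 6a and above here).

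**The case against.** The strongest reply is that this is one secondary sentence in a feasibility study that disclaims power, that its data collection is sound, and that the detail belongs in an analysis plan that is not at hand. Part of this stands. An analysis plan can decide how bereavement values enter the QALYs, and small numbers chosen for feasibility are acceptable in a pilot. It cannot, however, supply a control that the study does not collect, and the protocol itself fixes the causal and cost-effectiveness target.

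Some stronger readings are tempting but are not supported:

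- A reader might infer that there is no comparator of any kind. Carers do have a start value, and a historical comparison is planned for other scores. The gap is a concurrent control, and any named comparator for carer utility or costs.
- A reader might take 13 as the planned number of carers, or treat it as the error. The protocol sets no carer number. The figure is borrowed from a cohort with a stricter entry stage, in which 4 of 61 residents lived at home.
- A reader might infer that only residents are costed. Informal care and carer burden are included too.
- A reader might infer that savings from averted admissions will be claimed. The words are a parenthetical example whose meaning is unclear. The firm commitment, under Monthly follow up assessments, is to record actual admissions.
- A reader might infer that the carer QALY result is itself promised to commissioners. Objective 5 ties the commissioning process to costs.

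**Conclusion.** The point holds in a limited form. The stated purpose of the carer QALY analysis cannot be met by this design: the project's effect on carer utility is not identified, and no incremental cost or effect can be formed for a cost-effectiveness conclusion. This does not depend on any assumption about numbers. The same limit applies to any saving from averted admissions, if one is intended.

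Imprecision adds to the problem but does not create it. It amounts to a half-width of about 0.60 SD with 13 carers (0.77 to 0.51 SD across 9 to 17) and 0.37 SD with the maximum of about 30. The carer numbers rest on the earlier cohort's rate carrying over.

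The sentence also goes further than Objective 5, which is descriptive, and further than the sample-size rationale, which is feasibility. It should be corrected. It does not undermine the pilot's feasibility aims, and no data would be lost by correcting it.

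**What to change.** Replace the carer QALY sentence in Health economics with a descriptive aim consistent with Objective 5:

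- describe carer EQ-5D-5L utility over time with 95% CIs, separating values before and after bereavement;
- describe delivery costs and service use, for residents and carers;
- say that both are intended to inform a definitive trial.

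Add one sentence stating that no causal utility gain, ICER, cost-effectiveness conclusion or averted-admission saving will be claimed from this uncontrolled pilot. Clarify or remove the averted-admission example in the same section.

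The cost is a change of protocol wording. Visits, measures and recruitment stay as they are. The downside is a less favourable claim at the end of the pilot.

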Appendix 1: Compassion intervention manual

The Final Compassion Intervention Manual will be published with free access on the Marie Curie website (www.mariecurie.org.uk).

Appendix 16: Health Care Professional Qualitative Interview Schedule

HCP interview schedule Compassion Study (HCP interview schedule for intervention V1 09.01.2014)

Preamble

Thank you for agreeing to this interview. As you know we have introduced an Interdisciplinary Care Leader into the care home in which you work. The reason why we have invited you today for this discussion is to understand what your thoughts are on this service and if there was anything about this service that you think can be improved. Also, please be assured that the topics that we discuss today are strictly confidential and will remain completely anonymous.

Interview

Firstly, just for the purposes of the recording can you:

1. Describe your current role here
2. The type and amount of contact you have on a day to day basis with residents with severe memory problems (how severe these are, their roles and responsibilities)

Now I would like to talk about the role of the ICL and how it may have influenced the way you perform your job:

3. Tell me about how you found working with the ICL
4. Did the ICL influence the way you performed your role? If so, how? Can you provide some examples of how the ICL did this?
5. Do you think the ICL changed the care you provided to residents?

6. Did you find that it influenced any of the following:
 - a. Your knowledge of dementia
 - b. How you assess patients with severe memory problems
 - c. How you recognise symptoms such as pain and how you manage these symptoms?
 - d. Were you given any support and guidance on initiating and implementing advance care plans? If so, can you give us an example of when this happened?
 - e. The way you communicate/interact with patients who are no longer able to communicate
 - f. How comfortable you are about communicating with family members, including discussions about palliative care and death/dying
 - g. How you communicate with other HCPs

7. Tell me about your needs. Did the ICL influence the support that you receive in your role?
 - a. E.g., such as support following patient death

For care home manager: Did you notice any changes in the way your staff provided care to patients? How do you feel the ICL was received by your staff?

8. Is there anything about this service that can be improved? Is there anything that you would do differently if you were implementing this service?

Appendix 17: Family Carer Qualitative Interview Schedule

Family carer interview schedule (Compassion Study - Carer interview schedule for intervention V1 09.01.2014)

Preamble

Thank you for agreeing to this interview. The reason that we have invited you along for this discussion is to get an idea of the care and support that you and your relative have received over the last few months. If you feel that you need to stop or leave the room at any time please tell me. Whatever you tell me will be made anonymous for the purposes of the study.

Interview

I'd like to begin by asking you a little bit about X memory problems and your understanding of his/her illness

1. Tell me about X's illness and symptoms over the last few months
 - a. Both physiological and psychological needs

2. Tell me about the types of support or services has X received over the last few months
 - a. Formal or informal (Religion/spirituality)
 - b. Satisfaction

Now I'd like to ask you some questions about your needs as a carer:

3. How have you found dealing with X's illness over the last few months? What have you found particularly difficult?
 - a) Both physiological and psychological needs
 - b) Own mental health

4. Tell me about the support that you needed including emotional, psychological and social needs religious/spiritual needs. Were your needs assessed?

- a. If so, tell me about the services that you were offered to meet these needs (If yes, determine who this was offered by and when this took place)

5. Did you have any discussions with HCP's (GP, Consultant, nursing home staff etc) about (if yes, determine when these took place):
 - a. Course of illness
 - b. Additional information
 - c. Treatments – decision making – past and future
 - d. Inclusion of other family members

6. Has anyone discussed your thoughts if X's condition were to deteriorate? If so, who discussed these with you and when?
 - a) POA
 - b) DNAR
 - c) Place of death
 - d) ACP – Feasibility of carrying out another person's wishes

7. Has anyone discussed what the future holds for X?
 - a. i.e., religious beliefs/spirituality – Any recognition in the home?

8. We would also like to find out if the ICL has influenced the care and support that you and your relative have received over the last few months.
 - a. Tell me about any changes to the care and support that both you and X have received over the last few months
 - b. Tell me if these changes had a positive or a negative impact on you and X
 - c. Ways in which we can improve this service? How else can the ICL help you and your relative?

Additional question if patient has passed away: Can you tell me a little about what happened when X passed away?

The Compassion Programme: WS3- pilot study Version 1, 24th January 2014

- a) Did it all go smoothly?
- b) Were their end of life wishes met? (such as religious/spiritual wishes)
- c) Did you receive immediate and ongoing bereavement, emotional and spiritual support?
